## 7 DATA COLLECTION

Data specific to the sub-study will be collected from consent until 90 days at a number of key points by a member of the research team:

- At informed consent, enrolment and baseline investigations

- Eligibility and consent
- 0hr blood sampling
- 0hr vital signs
- Results of nearest serum lactate measurement (if taken as part of routine care)
- At 12 ( $\pm 4$ ) hours sampling
  - 12 hour blood sampling
  - Vital signs and ( $\pm 30$  minutes from time of sampling)
  - Results of nearest serum lactate measurement (if taken as part of routine care)
- At 24 ( $\pm 6$ ) hours sampling
  - 24 hour blood sampling
  - Vital signs (at  $\pm 30$  minutes from time of sampling)
  - Results of nearest serum lactate measurement (if taken as part of routine care)

All relevant intervention, outcome and follow up data will be collected as part of the ABC-Sepsis trial and a data sharing agreement will allow us to make use of this data.

## 7.1 SOURCE DATA DOCUMENTATION

Data will be collected from consent until final follow up visit.

Source data will either be study specific or routine clinical data. Study specific source data, including consent forms, eligibility criteria forms, and sampling details (e.g. timing of samples) will be recorded on the relevant pseudonymised source study data worksheets distributed to participating sites.

Clinical data, including physiological observations and blood samples taken as part of routine care, will be recorded according to local practice and transcribed onto the study data worksheets as agreed by site-specific source document plans.

## 7.2 CASE REPORT FORMS

Paper CRFs (study data worksheets) will be completed as the participant progresses through the study and then entered into a database on a trial database on a secure NHS computer. Scanned images of the worksheets may also be sent to the trial management team for quality assurance purposes.

Processing of samples will be recorded on 'processing logs', paper sheets which will record the time and date of processing, number of samples and person processing them. They will be shared with the trial management team in a similar manner to the study data worksheets.

Clinical outcome data will be collected as part of the ABC Sepsis study from NHS records and will include comorbidities; vital signs, routine blood results including baseline kidney function, liver function and albumin; relevant investigations or interventions including surgery, vasopressor use, renal replacement therapy, invasive ventilation, chest x-rays, prescriptions; time of start of ABC Sepsis IMP; length of stay including critical care, repeat hospitalisations, adverse events and decisions regarding treatment escalation planning and resuscitation. Detail will also be collected on the trial intervention including timing and volume of fluids. Length of stay and repeat hospitalisation will be recorded as part of follow up. These data will be shared with this sub-study in line with the ABC Sepsis data management plan for sharing and reuse.

## 7.3 TRIAL DATABASE

At regular intervals throughout the study, the site research teams will transcribe the paper worksheets into the trial database specifically developed for this purpose. This central database will be managed by the trial management team and kept on secure servers at the host institution. Scanned copies of the relevant paper worksheets (i.e. containing pseudonymised study data) may be requested from site teams for quality assurance.

Following data analysis, the database will be archived by the trial management team. This archived database will be stored indefinitely on secure host institution servers once user access has been disabled. Access to the archived database will be controlled by the Chief Investigator.

## 8 DATA MANAGEMENT

This trial will be coordinated from the Royal Infirmary of Edinburgh. Data will be collected at each site by local investigators and uploaded to the database. If a participant or their representative withdraws a previously given informed consent or refuses to consent for continuation in the trial, or if the participant dies and no participant consent is available, the patient's data will be handled as follows: Data collected up to the point of withdrawal will be used in an intention to treat analysis.

[figure not shown]
### 8.1 PERSONAL DATA

Local sites will also maintain a secure document as reference linking a participant's study ID with the personal information (including name, date of birth, hospital number, address, telephone number, sex at birth, GP information) of the participant. Where relevant, personal data of the personal representative will also be collected to obtain consent (including name, home address, telephone number).

The name, address and GP details will only be collected for the purposes of sending a letter to the GP informing them their participant is taking part, to send consent forms (if required), and to disseminate result of the trial (if the patient opts for this). This personal data will be kept at the study site.

Personal data will be stored by the study team on NHS computers (desktop and/or laptop). Computers will be password protected and kept in locked offices. All paper files containing personal data will be held in filing cabinets in NHS offices that will be locked when unattended. Access to the study documents will be by the study team only. Data will be entered by those staff delegated to do so on the delegation log held at site. Personal data will be stored for 5 years.

## 8.2 DATA INFORMATION FLOW

## 8.3 TRANSFER OF DATA

Personal data will not be transferred to any external individuals or organisations outside of the Sponsoring organisation.

Every effort will be made to make data available for legitimate re-use via existing University of Edinburgh systems, according to the FAIR principles [24]. Data stored on such repositories will only be those with which we can guarantee sufficient protection to participant confidentiality, as per University policies and governance systems.

## 8.4 DATA CONTROLLER

The University of Edinburgh and NHS Lothian are joint data controllers along with any other entities involved in delivering the study that may be a data controller in accordance with applicable laws (e.g. the site).

## 8.5 DATA BREACHES

Any data breaches will be reported to the University of Edinburgh and NHS Lothian Data Protection Officers who will onward report to the relevant authority according to the appropriate timelines if required.

# 9 STATISTICS AND DATA ANALYSIS

## 9.1 SAMPLE SIZE CALCULATION

Whilst a sample size of 300 has been calculated for the main ABC Sepsis study, as this sub-study is an exploratory analysis no sample size calculation has been conducted. The majority of existing work on cytokine and RNA response focuses on sampling dates in a different context: over the course of days to weeks in patients presenting to hospital with sepsis. Our work will provide a foundation upon which to build further larger studies. We aim to recruit a minimum of 70, which has been selected because it confers a greater than 90% likelihood of incorporating 30 or more participants in the smaller group, assuming equal likelihood of

randomisation to each arm. 30 is a consensus figure arrived at by expert co-authors of the study with experience in related work in critical care research [25]. We anticipate enrolment would not continue beyond 80 participants: at this sample size there is a 99% likelihood of including at least 30 participants in each arm.

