## Trial summary

Trial Title	MIS-ABC Sepsis: Mechanistic Inflammatory Sub-study embedded in the Albumin versus Balanced Crystalloid in Sepsis trial – ABC Sepsis
Study Acronym	MIS-ABC Sepsis
Trial Design	Prospective observational study
Trial Participants	Adult patients with community acquired sepsis recruited from the Emergency Department and Medical and Surgical Assessment Units in ~5 UK NHS Hospitals, who are enrolled into the ABC Sepsis trial
Planned Number of Participants	At least 70 participants
Planned Number of Sites	7
Countries Anticipated to be Involved in Trial	UK
Follow up Duration	Sampling period: 24 hours Follow up: 90 days
Total Planned Trial Duration	12 months
Primary Objective	To investigate whether the inflammatory response to community acquired infection/sepsis is dependent on the type of intravenous fluid used during resuscitation.
Primary Endpoint	No primary endpoint: analysis will be exploratory.
Secondary Objectives	1. To understand the inflammatory response in patients with community acquired infection/sepsis by the analysis of a panel of cytokines. 2. To evaluate whether the early inflammatory response to infection/sepsis at the time of presentation to secondary care predicts clinically important outcomes. 3. To investigate whether transcriptomic analysis can provide an explanation for varying physiological response to fluid therapy and clinical outcomes in infection/sepsis.
Secondary Endpoints	No specific secondary endpoints: analysis will be exploratory.
Lay Summary of Trial	This is a sub-study looking to understand how the immune response in patients with infection changes during the early stages of the illness, as well as after intravenous fluid treatment. Participants in the main trial will be given one of two types of fluid (Human Albumin Solution (HAS) and Balanced Crystalloid) via a drip when they present to the hospital with severe infection (sepsis). The main trial is assessing which fluid is better, and we are going to take three blood samples around the time people come to hospital to see what happens to their immune system as a result of the infection and fluid treatment. We hope our findings will explain why one fluid might be better than another. It may also give us an important information about whether we can predict which people might get sicker despite treatment.

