## 4 STUDY POPULATION

### 4.1 NUMBER OF PARTICIPANTS

We aim to recruit at least 70 patients from approximately 7 sites, ideally with at least 30 patients from each intervention arm of ABC Sepsis. The main study aims to recruit 300 patients from approximately 15 sites. Site selection for this sub-study will depend on whether that site has capacity to do so and will likely focus on sites who have demonstrated success with recruitment to the main study. Recruitment will take place over a period of around 6 months.

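### Section 9.1 justifies 70 participants by a more than 90% chance that the smaller arm reaches 30; with equal, independent allocation the chance is about 81%

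*Protocol*

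**What the plan says.** Section 9.1 states that no formal sample size calculation was done, because the sub-study is exploratory. It then gives one quantitative reason for setting the minimum at 70, namely that "it confers a greater than 90% likelihood of incorporating 30 or more participants in the smaller group". The condition attached is that a participant is as likely to be randomised to one arm as to the other. The figure of 30 is described as a consensus among the expert co-authors.

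The same section sets an expected ceiling, "We anticipate enrolment would not continue beyond 80 participants", and adds that "at this sample size there is a 99% likelihood of including at least 30 participants in each arm".

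The minimum and the per-arm target recur elsewhere. The trial summary gives "At least 70 participants", and section 4.1 repeats the 70, "ideally with at least 30 patients from each intervention arm of ABC Sepsis".

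**The concern.** A statement about the smaller group is a statement about both arms. With 70 participants, the smaller group can fail to reach 30 in two ways: too few in the albumin arm or too few in the crystalloid arm. A probability that counts only one of these is too high, and the figure in section 9.1 looks like such a one-arm probability.

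This matters because it is the only numerical argument for the minimum of 70; no power calculation stands behind it. The primary objective (section 2.1.1) asks whether the inflammatory response depends on the type of fluid, so the size of the smaller arm limits that comparison. A reader of section 9.1 would believe that stopping at 70 carries less than a 10% risk of missing 30 in an arm.

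**Working it through.** **Inputs, all from section 9.1:** minimum N = 70; expected ceiling N = 80; target of 30 in each arm; probability 0.5 of either arm for each participant. Independence between participants is added here as the natural reading of the equal-likelihood assumption.

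Let X be the number in one named arm, X ~ Bin(N, 0.5).

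**Reproducing the protocol's figures.** The probability that one named arm reaches 30 is P(X ≥ 30):

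- N = 70: 0.9059
- N = 80: 0.9908

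These match the stated figures of more than 90% and 99%. The sizes fit too: 70 is the smallest N at which this one-arm probability passes 90% (N = 69 gives 0.8858), and 80 is the smallest at which it passes 99% (N = 79 gives 0.9881).

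**The event the protocol describes.** Both arms reach 30 when 30 ≤ X ≤ N − 30. By symmetry,

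P(30 ≤ X ≤ N − 30) = 1 − 2·P(X ≤ 29) = 2·P(X ≥ 30) − 1.

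For N = 70 this is P(30 ≤ X ≤ 40) = 2 × 0.9059 − 1 = 0.8118. The probability of a shortfall is therefore 1 − 0.8118 = 0.188.

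| N | One named arm ≥ 30 | Both arms ≥ 30 |
|---|---|---|
| 70 | 90.6% | 81.2% |
| 72 | 93.8% | 87.5% |
| 73 | 95.0% | 89.9% |
| 74 | 96.0% | 91.9% |
| 76 | 97.5% | 95.0% |
| 78 | 98.5% | 96.9% |
| 80 | 99.1% | 98.2% |

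The both-arms probability first exceeds 90% at N = 74 (0.9195; N = 73 gives 0.8994).

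**How large the shortfall would be at N = 70.** The smaller group is 29 with probability 6.9%, 28 with 4.7%, and 27 or fewer with 7.2%. The largest smaller-group size that 70 participants deliver with more than 90% probability is 28 (92.8%; for 29 it is 88.0%).

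**Other ways of computing the N = 70 figure:**

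- Normal approximation: 0.811 with continuity correction, 0.768 without.
- Drawing 70 at random from a main trial of 300 (section 4.1), assumed to be split exactly 150/150: 0.867.
- Drawing 70 at random from a pool of 140 split exactly 70/70, where 140 is an assumption (300 patients over about 15 sites, times about 7 sites): 0.937.
- Site-stratified permuted blocks with every main-trial patient at each site joining, also an assumption: about 1.

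Only the last two exceed 90%, and both need balance that the protocol does not state.

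**The case against.** The strongest objection is that equal likelihood of either arm does not by itself mean independent allocation. Blocked or minimised 1:1 randomisation also gives each participant an equal chance of either arm, and it keeps the arms closer in size. The main trial's method is not described in this document, and under strong balance the probability at 70 could exceed 90%. This stands as a limit on the exact value of 81%. It does not rescue the sentence, which relies on equal likelihood alone and mentions no balancing. Balance in the main trial also need not carry over: joining the sub-study is optional (section 5.1), only about 7 of about 15 main-trial sites take part (section 4.1), and in Scotland the consent route is narrower than in the main trial (section 5.2.3). Even a simple draw from an exactly balanced 300 gives only 86.7%.

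A second objection is that the protocol shows no calculation, so the use of a one-arm probability is inferred. That is fair. The inference is well supported, because it reproduces both stated figures and both chosen sizes, but the 81.2% does not depend on it.

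A third is that little turns on the number. Sections 2.2 and 9.1 set no endpoints and no power, 30 is an ideal, 70 is a floor, and no analysis in section 9.2 changes between 28 and 30 per arm. This limits the consequence but does not make the stated figure right.

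**Conclusion.** The figure given as the reason for 70 is wrong as written. With independent 1:1 allocation, 70 participants give an 81.2% probability of at least 30 in the smaller group, about 9 percentage points below the stated floor of 90%. The risk of a shortfall at the minimum is about 19%, roughly twice what the text implies. The companion figure for 80 (98.2% against a stated 99%) is off by 0.8 points, which is immaterial alone.

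The result rests on independent allocation with probability 0.5, and a documented balance-forcing method that carries over to the sub-study would change it. The practical effect is modest: the risk falls quickly as recruitment moves towards 80, and shortfalls at 70 are usually a few participants. It should still be corrected, because it is the stated basis for the minimum.

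**What to change.** Restate the justification in section 9.1, for example: *Assuming independent 1:1 allocation, 70 participants give about an 81% probability, and 80 participants about a 98% probability, of at least 30 in each arm.* If the main trial's method forces balance and the sponsor wants to rely on it, name the method, say why the balance carries over to the sub-study, and recompute both figures on that basis.

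The restatement is sufficient; the minimum need not change. If the sponsor wishes to keep a probability above 90% at the minimum, the smallest value that gives it under independent allocation is 74 (91.9%). That adds four participants to the minimum, within the 70 to 80 already foreseen, and the trial summary and section 4.1 would need matching edits.

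The restatement alone is a change of wording in one section, at the price of a less favourable figure. If it is handled as an amendment, it follows the route in section 12.1: Chief Investigator and sponsor review, then the REC and local R&D. It alters no analysis and nothing in patient care.

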## 9.2 PROPOSED ANALYSES

This project is primarily an exploratory analysis. We will report results by group as defined by the treatment arm into which they are enrolled, as well as by key outcomes (e.g. mortality at 30 days, admission to ICU). No interim analyses will be conducted.

Analysis will be conducted, across treatment arms, of individual biomarkers as part of our cytokine panel, whether at individual timepoints or in terms of the change, and rate of change, from baseline results. It will also incorporate analysis of grouped variables (e.g. 'pro-inflammatory cytokines' versus 'anti-inflammatory cytokines', or those known to be representative of specific pathophysiological damage like endothelial damage), again at individual timepoints or in terms of the change, and rate of change, from baseline. Further grouping may be taken, depending on the spread of our physiological data, to determine differences between 'responders' to fluid challenge versus 'non-responders' in either treatment arm.

Taken as a whole, we will assess the accuracy of these biomarkers as predictors of our key clinical endpoints, with consideration of sensitivity, specificity and positive or negative predictive values. Receiver operator characteristic analysis will be explored for biomarkers with significant biological plausibility or which show promise in the preceding analysis. Transcriptomic data from RNA-seq will be interrogated to determine changes in RNA abundance at the gene level between sample points and by treatment arm, as well as at the transcript isoform level.

Using the inclusion criteria mentioned before, it is plausible that we will include patients who ultimately are diagnosed with a pathology other than sepsis as a reason for their presentation to hospital. The inclusion of the results of such patients in the described analyses will be decided on discussion with the broader study team in the context of the frequency of this occurrence as well as the potential bias this might incur with the specific analysis.

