### ***Types of IV fluid***

There are two types of commonly used IV fluid in the resuscitative management of patients with Sepsis. These are crystalloid (balanced and unbalance) and large molecule colloid fluids.

Balanced crystalloids contain salts at physiological concentrations found in healthy humans, and are advocated as first line for sepsis by NICE and the surviving sepsis guidelines [11]. Resuscitation with crystalloid (either balanced or unbalanced) is the preferred treatment of choice for shocked septic patients according to an international survey [12].

Albumin, used in this setting as 5% Human Albumin Solution (HAS), is a colloid fluid which NICE directs clinicians to consider for patients with sepsis and shock [13]. However its specific role in sepsis management is, undefined and is largely clinician dependent in the absence of definitive evidence for its use.

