### ***The Evidence for Albumin***

Albumin is a protein produced by the liver which is responsible for 80% of the intravascular cellular oncotic pressure. Other functions include a pivotal role in acid-base homeostasis, transport of a number of key molecules including drugs, and scavenging of reactive oxygen species [14].

Hypoalbuminaemia in sepsis is a poor prognostic factor for mortality, probably reflecting the severity of disease through endothelial dysfunction and decreased serum albumin half-life [15,16].

A small number of trials have examined the use of albumin in sepsis. The SAFE trial randomised ICU patients to 4% albumin or normal saline for intravascular fluid resuscitation for 28 days, and found no difference between 28-day mortality, and although a pre-specified

CR007-T02 v4.0

Page 6

subgroup analysis of patients with severe sepsis signalled a benefit for albumin, this too did not reach statistical significance [17]. The ALBIOS study randomised patients with severe sepsis to either 20% albumin and crystalloid fluid or crystalloid fluid alone, with the former arm targeting serum albumin levels of above 30g/L or more. Again, this study found no significant difference between 28 day mortality [18]. However, a subsequent secondary analysis in patients with severe shock and raised lactate identified a survival benefit in the albumin arm reaching statistical significance [19]. A 2014 meta-analysis which included these, amongst three other trials, found a significant improvement in mortality for patients with severe septic shock, and trends towards benefit for those with severe sepsis against crystalloid [20].

These studies have demonstrated safety of albumin but are yet to demonstrate a significant survival benefit in ICU patients. Although undoubtedly these studies select for the sickest patients with sepsis, it is possible that studies in such environments miss a cohort of severely unwell patients who are not suitable for ICU but who may benefit in a similar way from the treatment. Intervention at admission to ICU may even be too late to interrupt the downward-spiralling sequelae of septic shock like end organ failure in some patients.

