We hypothesise that different types of intravenous fluids used in resuscitation (albumin versus balanced crystalloid) may mediate different pro and anti-inflammatory response as measured by these cytokines. We also hypothesise that plasma levels of these cytokines, measured at time of ED admission, will enable improved differentiation of patients with suspected sepsis who are at high risk of deterioration

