## **1.2 RATIONALE FOR STUDY**

Currently, there is controversy about the optimal fluid choice in patients presenting to hospital with sepsis. Understanding how each fluid type affects the underlying inflammatory process may provide a mechanistic argument for clinician choice, future research and professional recommendations.

MIS-ABC Sepsis is a sub-study of the ABC-Sepsis trial, a pilot feasibility trial recruiting patients with community acquired infection/sepsis with a NEWS2 score of five or more and randomising the participants to receiving either balanced crystalloid or 5% HAS as the intravenous resuscitation fluid up to six hours after randomisation.

MIS-ABC Sepsis will take serial blood samples from a small number of these participants, at hospital presentation and at two further points early during the patient's admission, to allow analysis of how inflammation changes during their course of illness. Investigating temporal change and differences between treatment arms of the main study will allow a nuanced analysis of the interplay between severity of illness, physiological changes over time and any potential differences between fluid treatment arm.

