## 2 STUDY OBJECTIVES

### 2.1 OBJECTIVES

#### 2.1.1 Primary Objective

To investigate whether the inflammatory response to infection/sepsis is dependent on the type of intravenous fluid used during resuscitation in the Emergency Department.

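### Plasma cytokine contrasts between a colloid arm and a crystalloid arm may partly reflect dilution, and the protocol secures no dilution marker with the 12 h and 24 h samples

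*Protocol*

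**What the plan says.** The primary objective (protocol section 2.1.1) is to find out "whether the inflammatory response to infection/sepsis is dependent on the type of intravenous fluid used during resuscitation". The background hypothesis is that the fluids "may mediate different pro and anti-inflammatory response as measured by these cytokines". Section 6.4 takes the cytokines from the spun EDTA tube and stores that fraction as plasma, so each result is an amount per volume of plasma.

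The main trial is described in section 1.2 as "randomising the participants to receiving either balanced crystalloid or 5% HAS as the intravenous resuscitation fluid up to six hours after randomisation". The background says that human albumin solution "is a colloid fluid which NICE directs clinicians to consider for patients with sepsis and shock", and that albumin is "responsible for 80% of the intravascular cellular oncotic pressure".

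Section 6.2 takes the baseline sample before or at the start of trial fluid, and the later samples at 12 ± 4 h and 24 ± 6 h after enrolment. Section 9.2 then plans: "Analysis will be conducted, across treatment arms, of individual biomarkers as part of our cytokine panel". It covers single time points, change and rate of change from baseline, and grouped pro- and anti-inflammatory variables.

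The only laboratory value that section 7 transcribes with each sample is lactate: "Results of nearest serum lactate measurement (if taken as part of routine care". Section 7.2 adds data shared from the main trial. These include routine bloods (baseline kidney function, liver function and albumin are named) and the timing and volume of trial fluid. Dilution, plasma volume, haemoglobin and haematocrit are not mentioned anywhere in the protocol.

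**The concern.** A concentration is an amount divided by a volume, and the intervention here is itself a volume of fluid. If one fluid stays in the circulation longer, cytokine concentrations in that arm fall without any change in the amount of cytokine present. A common dilution factor acts in the same direction on every plasma cytokine, so it could look like a general difference in inflammation between arms, or mask a true difference in the opposite direction.

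The usual safeguards do not help. The shift arises after randomisation and because of the allocated fluid. The baseline sample is taken too early to carry it. Because it is a bias, a larger sample does not shrink it.

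This matters because section 1.2 wants a mechanistic argument to inform clinician choice, further research and professional recommendations. For that use, the reader must know whether a difference in concentration is a difference in response.

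**Working it through.** The protocol gives no figure on this point, so there is none to reproduce. The check has three steps.

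**1. Form of the bias.** Let *M* be the circulating amount of a cytokine and *V* the plasma volume at sampling, so that *C* = *M*/*V*. With *R* = *V*(albumin)/*V*(crystalloid),

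ln *C*(albumin) − ln *C*(crystalloid) = ln[*M*(albumin)/*M*(crystalloid)] − ln *R*.

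If the amounts are equal, the whole contrast is −ln *R*, the same for each cytokine.

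**2. Timing.** The treatment phase lasts 6 h from randomisation (section 3). If enrolment coincides with randomisation, as section 5.1 intends, the second sample (8-16 h) falls 2-10 h after that phase and the third (18-30 h) falls 12-24 h after it. Any dilution effect has between 2 and 24 h to fade.

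**3. Size, under assumptions.** None of the inputs below is in the protocol: *R* from 1.02 to 1.20, log-scale SD of 0.5 to 1.5, and 35 per arm (half of the minimum of 70). The fall in albumin-arm concentration is 1 − 1/*R*. The chance of a nominal two-sided p < 0.05 from dilution alone is Φ(*q* − 1.96) + Φ(−*q* − 1.96), where *q* = ln *R* / (SD × √(2/35)). It is 5% when *R* = 1. The last column is a mean score of all 14 listed cytokines with log SD 1.0 and pairwise correlation 0.3. Its SD is √((1 + 13 × 0.3)/14) = 0.59.

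| *R* | Fall in concentration | One cytokine, SD 0.5 | SD 1.0 | SD 1.5 | 14-cytokine score |
|---|---|---|---|---|---|
| 1.02 | 2.0% | 5.3% | 5.1% | 5.0% | – |
| 1.05 | 4.8% | 6.9% | 5.5% | 5.2% | 6.4% |
| 1.10 | 9.1% | 12.5% | 6.8% | 5.8% | 10.3% |
| 1.20 | 16.7% | 33.2% | 11.9% | 8.0% | 25.2% |

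Worked case: *R* = 1.10 and SD 1.0 give *q* = 0.0953/0.239 = 0.40 and a rate of 6.8%. With correlation 0.6 the score's rates at *R* = 1.10 and 1.20 drop to 7.9% and 16.1%. Averaging removes noise but not a shared shift, which is why grouped scores are more exposed.

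**Direction.** Suppose a starting plasma volume of 3 L, 1-2 L of trial fluid, and 20-30% of crystalloid and 50-90% of albumin solution retained at sampling. With equal volumes given, the albumin-to-crystalloid concentration ratio runs from 3.3/3.5 = 0.943 to 3.4/4.8 = 0.708. With unequal volumes from the same ranges (2 L crystalloid at 30%, 1 L albumin at 50%) it is 3.6/3.5 = 1.03, and the sign reverses.

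**The case against.** **Much of this belongs in a statistical analysis plan.** Correction formulas and ratio readouts are analysis detail, and the plan is not shown. That stands for the analysis. It does not stand for the data: no plan can correct for dilution at 12 h and 24 h unless a marker was recorded then.

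**The marker may already exist.** A reader might infer from section 7 that haemoglobin will be unavailable. The documents do not support that. The list of shared main-trial data in section 7.2 is open-ended, and the main-trial case report form is not at hand. What can be said is that nothing shown secures haemoglobin or haematocrit at the later time points. The named substitutes fall short: serum albumin is infused in one arm, and infused volume is not retained volume.

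**Different plasma expansion is an inference.** A reader might take it as the stated rationale of the main trial. No section says so. The protocol describes that trial as a feasibility study and lists several other roles for albumin. It also notes raised capillary permeability in sepsis, which argues against assuming high retention.

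**The effect may be small.** Cytokines are produced and cleared continuously, so passive dilution is transient, and sampling comes 2-24 h after the treatment phase. This stands, and it is a reason to measure dilution rather than assume it.

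**The raw contrast is valid in itself.** As a randomised comparison of plasma concentrations it is a legitimate total effect, and the study is exploratory with no endpoints. This also stands. The difficulty lies only in reading that contrast as inflammatory response. RNA sequencing by arm would be less exposed to dilution, but section 6.4 says it is not yet funded.

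**Conclusion.** The point holds as a cheap improvement, not as an error that invalidates the comparison. The primary objective is read from plasma concentrations after two fluids that may leave different plasma volumes, and the design cannot separate dilution from response without a marker at each sample.

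The size is unknown. On the assumed 2-20% volume difference with equal cytokine amounts, the shift is about 2-17%. At log SD 1.0 the false-signal rate for one cytokine rises from 5% to at most 11.9%; for the illustrative 14-cytokine score it reaches 25.2% at the top of that range.

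Two stronger readings are tempting and not supported. One is that every cytokine would be 6-29% lower in the albumin arm. That range (from the ratios 0.943 and 0.708) needs assumed retention, equal volumes in both arms and a closed cytokine pool, and its direction reverses once the volumes differ. The other is that an arm difference should count as inflammatory only if it survives correction. Such a rule could reject a true uniform effect and does not suit an exploratory study.

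**What to change.** 1. **Section 7.** At 0, 12 and 24 h, add the nearest haemoglobin and haematocrit, if taken as part of routine care, beside lactate. Alternatively, confirm in the protocol that the main trial shares them at those times.
2. **Section 9.2 (or the analysis plan).** Report each arm contrast raw and, as a sensitivity analysis, corrected for plasma-volume change from baseline. If circulating haemoglobin is conserved, the plasma-volume ratio is (Hb₀/Hbₜ) × (1 − Hctₜ)/(1 − Hct₀), and the corrected concentration is the measured one times that ratio.
3. **Supplementary readout.** Add a within-sample log ratio of pro- to anti-inflammatory cytokines, in which a common dilution factor cancels.
4. **Interpretation.** State that uncorrected differences alone cannot separate dilution from response. Set no pass/fail rule.

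**Cost.** One routine result transcribed per sampling time and a few lines of analysis text; no extra blood.

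**Downsides.** Haemoglobin may be missing, or altered by bleeding or transfusion. Correction may over-adjust cytokines with fast turnover. Ratios also cancel a genuine uniform change. The corrected and ratio results should therefore accompany the raw contrast, not replace it.
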